9.7. EXACERBATION VISIT/CONTACT

Subjects will be trained by the Investigator to recognise signs and symptoms of NCFB pulmonary exacerbations. At each post-randomisation visit the patient will be reminded about how to recognise symptoms of a NCFB pulmonary exacerbation and instructed to contact the site as soon as they have experienced these symptoms for 24 hours. If feasible, the subject will be asked to attend the clinic at their earliest convenience. If it is not practical for the subject to make an additional clinic visit then relevant information will be collected via phone and the subject will be asked to provide a sputum sample to the clinic in a manner most appropriate to the subject.

Any episodes of pneumonia during the trial should be considered as pulmonary exacerbations and will also require a clinic visit, if feasible. Episodes of pneumonia which are radiologically confirmed and/or requiring intravenous antibiotics and/or hospitalisation will be considered as severe pulmonary exacerbations. Adverse Events of COVID-19 with symptoms of an exacerbation, requiring antibiotics during the course of the study should be considered as pulmonary exacerbations for reporting in the eCRF.

The Investigator will decide if symptoms represent a NCFB pulmonary exacerbation meeting the protocol-defined criteria or not and on the appropriate course of action. It will be clinically determined if the subject requires systemic antibiotic therapy (oral or intravenous) in addition to IMP administration or whether IMP administration should be temporarily interrupted (see below). Treatment of a NCFB pulmonary exacerbation will follow current treatment regimens used in the respective participating trial site.

If the symptoms represent a NCFB pulmonary exacerbation, regardless of whether it meets the protocol definition or not, these should be considered as pulmonary exacerbations for reporting in the eCRF.

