11.1. CONCOMITANT MEDICATION

Concomitant medication for NCFB pulmonary exacerbations allowed in the study include:

- acute and/or short-term administration of oral/intravenous bronchodilators and corticosteroids, if required;
- systemic (oral or intravenous) antibiotics according to current treatment regimens used at the participating sites;
- acute and/or short-term administration of oxygen therapy/ventilator assistance.

At each visit subjects will be asked about any concomitant medications they have taken to self-treat at home. Concomitant medication prescribed by the Investigator for a pulmonary exacerbation will be documented.

The following will be recorded:

- Dates of administration including start and end dates;
- Dosage information including dose and frequency;
- Reason for use.

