2.1 Primary Endpoint

The primary endpoint of this trial is the mean annual NCFB pulmonary exacerbation rate.

A pulmonary exacerbation is defined as the presence concurrently of at least 3 of the following 8 symptoms/signs for at least 24 hours:

- Increased cough;
- Increased sputum volume and/or consistency;
- Increased sputum purulence;
- New or increased haemoptysis;
- Increased wheezing;
- Increased dyspnoea;
- Increased fatigue/malaise;
- Episodes of fever (temperature $\geq 38^{\circ}\text{C}$);

And it is clinically determined that the subject requires and is prescribed systemic antibiotic therapy.

The start date of a protocol-defined pulmonary exacerbation will be taken as the first day that at least 3 of the pre-defined 8 symptoms/signs occurred concurrently for at least 24 hours, as determined by the Investigator, as documented by the start date of the corresponding AE in the eCRF AE form.

Resolution of a pulmonary exacerbation is defined as the date of completion of the required course(s) of systemic antibiotic treatment and/or the Investigator's judgement that the NCFB pulmonary exacerbation has resolved, as documented by the end date provided for the corresponding AE in the eCRF AE form, whichever is the later of the two dates. The exacerbation end date will be reported at the next scheduled visit or by phone. A new pulmonary exacerbation is only considered to occur if there are at least 14 days between the end of the course of systemic antibiotics and the onset of new qualifying symptoms.

Any episodes of pneumonia during the trial should be considered as pulmonary exacerbations. Episodes of pneumonia which are radiologically confirmed and/or requiring intravenous antibiotics and/or hospitalisation will be considered as severe pulmonary exacerbations. Adverse Events of COVID-19 with symptoms of an exacerbation, requiring antibiotics during the course of the study are considered as pulmonary exacerbations. All pulmonary exacerbations must have the associated

CONFIDENTIAL

Sponsor:	Zambon S.p.A.	Protocol Number:	Z7224L02
----------	---------------	------------------	----------

Pulmonary Exacerbation, Pulmonary Exacerbation Symptoms and Systemic Antibiotic Therapy forms entered into the eCRF, and linked to the corresponding AE.

The treatment of pulmonary exacerbations will follow current treatment regimens used at the respective participating investigational site.

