A supportive analysis will be conducted using an alternative definition of NCFB pulmonary exacerbation. The re-classification of exacerbations will be done in a blinded fashion (before database lock). Alternative definition of pulmonary exacerbation: deterioration in three or more of the following key symptoms for at least 48 hours:

- Cough;
- Sputum volume and/or consistency;
- Sputum purulence;
- Breathlessness and/or exercise tolerance (dyspnoea);
- Fatigue and/or malaise;
- Haemoptysis;

And a physician determines a change in bronchiectasis treatment is required when other potential causes of clinical deterioration have been discounted.

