- if the day and the month are missing, then the date will not be imputed and the duration will be classified as “Not Evaluable”.

Resultant dates will be discussed during the blind review meeting and documented in the Blind Data Review and Analysis Sets Report.

The above summary/analysis will be performed using the mITT Population and, where appropriate, the PP Population. Results for the PP Population will be considered as supportive.

4.7.4.1 **CCI** Analysis Using Alternative Definition of NCFB Pulmonary Exacerbation

A **CCI** analysis will be conducted using an alternative definition of NCFB pulmonary exacerbation for the mITT Population. The re-classification of pulmonary exacerbations will

CONFIDENTIAL

Sponsor:	Zambon S.p.A.	Protocol Number:	Z7224L02
----------	---------------	------------------	----------

be done during the blind review meeting and documented in the Blind Data Review and Analysis Set Report.

In this CCI analysis, a NCFB pulmonary exacerbation is defined as deterioration in three or more of the following key symptoms for at least 48 hours:

- [REDACTED]
- [REDACTED]
- [REDACTED]
- [REDACTED]
- [REDACTED]
- [REDACTED]

And:

CCI [REDACTED]
[REDACTED]
[REDACTED]

Subjects experiencing NCFB pulmonary exacerbations according to this alternative definition will be identified as those subjects having:

- An AE on the eCRF Adverse Events form with a MedDRA coded Preferred Term of “infective exacerbation of bronchiectasis” that is at least 48 hours in duration (i.e. stop date of AE – start date of AE + 1 ≥ 2);
- At least 3 of the above symptoms on the eCRF Pulmonary Exacerbation Symptoms form for the Pulmonary Exacerbation Number corresponding to that AE, where those symptoms all occur between the start and stop dates of the AE;
- At least 1 therapy on the eCRF Systemic Antibiotic Therapy form for the Pulmonary Exacerbation Number corresponding to that AE.

Analysis will be conducted following the same rules and methods as detailed above for the main definition of NCFB pulmonary exacerbations.

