4.7.6.4 CCI

CCI documented on the CCI of the CCI F are presumed to include episodes of pneumonia given the requirement for intravenous antibiotics. Data will be reviewed during the blind review meeting and documented in the Blind Data Review and Analysis Sets Report.

A CCI will be defined as treated with systemic antibiotic therapy if a treatment is recorded in the Systemic Antibiotic Therapy form of the eCRF.

The number of CCI will be analysed using a negative binomial model in the same manner as described for the primary endpoint (which includes all CCI) in Section 4.7.4. The annualised CCI

CONFIDENTIAL

Sponsor:	Zambon S.p.A.	Protocol Number:	Z7224L02
----------	---------------	------------------	----------

CCI [redacted] rate estimates will be extracted for each treatment group from the model along with the rate ratio and its 95% CI and p-value..

The above summary/analysis will be performed using the mITT Population.

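### The alternative exacerbation definition turns on a change of bronchiectasis treatment, but its algorithm can count only episodes with a systemic-antibiotic record

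*SAP*

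**What the plan says.** SAP 2.1 states both definitions. The treatment limb of the primary event is: "And it is clinically determined that the subject requires and is prescribed systemic antibiotic therapy". The alternative event needs "deterioration in three or more of the following key symptoms for at least 48 hours", drawn from a list of six, with this treatment limb: "And a physician determines a change in bronchiectasis treatment is required when other potential causes of clinical deterioration have been discounted". It names no drug class and no route.

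SAP 4.7.4.1 then says how events under the alternative definition are found in the data. There are three conditions: an AE coded to infective exacerbation of bronchiectasis that passes a duration rule; at least three of the listed symptoms falling within the AE dates; and "At least 1 therapy on the eCRF Systemic Antibiotic Therapy form for the Pulmonary Exacerbation Number corresponding to that AE". SAP 4.7.6.4, dealing with another endpoint, shows what a record on that form means: an event "will be defined as treated with systemic antibiotic therapy if a treatment is recorded in the Systemic Antibiotic Therapy form of the eCRF".

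Two protocol sections bear on whether other episodes exist. Protocol 11.1 lists, next to systemic antibiotics, "acute and/or short-term administration of oral/intravenous bronchodilators and corticosteroids, if required" and oxygen or ventilatory support as allowed treatment for an exacerbation. Protocol 9.7 says of episodes judged to be exacerbations: "regardless of whether it meets the protocol definition or not, these should be considered as pulmonary exacerbations for reporting in the eCRF".

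**The concern.** The SAP writes one definition and programs another. In words, the alternative definition varies three things against the primary: the symptom list, the duration and the treatment decision. As programmed, the treatment decision does not vary, because every counted episode still needs a systemic antibiotic.

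Whether to prescribe a systemic antibiotic is a clinical judgement, and the protocol leaves exacerbation treatment to each site's own regimens (Protocol 9.7 and 10.1.5). Someone who reads Table 14.2.1.1.3 beside SAP 2.1 would take it that this limb had been varied, and would read agreement with the primary analysis as reassurance on it. The table cannot give that reassurance. If the treatment groups differed in how often an episode was managed without a systemic antibiotic, neither analysis would show it.

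**Working it through.** The SAP states no figure for this analysis, so there is nothing to reproduce. The check sets the texts side by side and then tests their logic.

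| Limb | Primary (SAP 2.1) | Alternative as written (SAP 2.1) | Alternative as programmed (SAP 4.7.4.1) |
|---|---|---|---|
| Symptoms | 3 of 8, concurrent | 3 of 6 | 3 of the listed symptoms within the AE dates |
| Duration | 24 hours | 48 hours | AE duration rule |
| Treatment | systemic antibiotic required and prescribed | treatment must change, per physician | record on the Systemic Antibiotic Therapy form |
| Other causes | not mentioned | discounted | no explicit test; AE must carry one Preferred Term |

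The treatment limb is blacked out where SAP 4.7.4.1 repeats the definition, but it is legible in SAP 2.1. The comparison uses only legible text.

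**Logic.** Take five yes/no features of an episode: S (enough symptoms), D (long enough), A (systemic antibiotic given), O (other treatment change), C (other causes discounted). S and D are treated as the same in definition and algorithm, so that only the treatment limb is tested.

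- Written definition: S and D and C and (A or O).
- Algorithm: S and D and A.

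Of the 2^5 = 32 combinations:

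- 3 meet the written definition (S, D and C present, with A only, O only, or both).
- 4 are accepted by the algorithm (S, D and A present, with O and C free).
- 1 meets the definition and is rejected: S, D, C and O present, A absent.
- 0 are accepted without A.

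These count logical cases, not patients. The Preferred Term condition, left out here, can only narrow the algorithm further, so the zero stands.

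**Could the rejected case be in the data?** Protocol 9.7 requires reporting of exacerbations that miss the protocol definition. SAP 4.7.4 refers to an eCRF question on whether the protocol-defined criteria are met, so the database can hold episodes answered no. Protocol 11.1 allows non-antibiotic treatment and has its dates and reason for use recorded. SAP 4.6 names the two medication forms, Prior and Concomitant Medications and Systemic Antibiotic Therapy. The algorithm reads only the second.

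**Size.** If a share q of episodes meeting the written definition is managed without a systemic antibiotic, the algorithm captures 1 − q of them. The documents do not give q. Purely for illustration, q = 5%, 10% or 20% means 95%, 90% or 80% captured; q = 0 means no loss.

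**The case against.** The strongest reply is that the rejected case may hardly occur. SAP 2.1 says that all pulmonary exacerbations must have a linked Systemic Antibiotic Therapy form. The visit checks for unreported events (Protocol 9.3 to 9.5, event name blacked out) ask about antibiotics prescribed elsewhere. Capture of episodes without antibiotics is therefore probably incomplete, and their number could be close to zero. This stands as a limit on size. It does not make the algorithm implement the definition, and it sits awkwardly with the wider reporting rule in Protocol 9.7.

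Reclassification is also to be done at the blind review meeting, which gives some discretion. But the listed criteria offer no non-antibiotic route for the meeting to apply.

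A reader might go further in three ways that the documents do not support:

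- That the analysis was designed to relax the prescribing criterion. The SAP gives no purpose for it. Only the treatment limb is wider; the 48-hour requirement, the loss of wheeze and fever and the discounting of other causes are all tighter.
- That the algorithm can only remove antibiotic-treated events from the primary count. It does not ask for concurrent symptoms, whereas the primary definition does. An antibiotic-treated episode with staggered symptoms could fail the primary definition and enter here.
- That the loss can be put as a number of events. With 287 subjects (taken as 143 placebo and 144 active), a full year each and a placebo rate of 1.09, the protocol's 35% effect gives 143 × 1.09 + 144 × 1.09 × 0.65 ≈ 258 events. Its 30% effect gives 143 × 1.09 + 144 × 1.09 × 0.70 ≈ 266, so 258 is no ceiling. More to the point, nothing in the documents supplies the share to apply, or shows that such episodes would meet the symptom and duration limbs.

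**Conclusion.** The mismatch is real and follows from the text alone. The alternative definition is written around a change in treatment and programmed around a systemic-antibiotic record, so a qualifying episode managed in any other way is excluded by construction. Table 14.2.1.1.3 would carry a label it does not earn. It can speak to the altered symptom and duration criteria, but not to the antibiotic-prescribing criterion.

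The number of episodes affected is unknown and may be small. The analysis is supportive, and the primary result does not depend on it. The conclusion assumes that the definition repeated in SAP 4.7.4.1 under redaction is the one printed in SAP 2.1; the legible lead-in to the symptom list matches.

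**What to change.** Reconcile SAP 2.1 and SAP 4.7.4.1 in one of two ways.

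(a) Implement the written definition. Widen the third condition in SAP 4.7.4.1 so that it also accepts a new or changed bronchiectasis treatment on the Prior and Concomitant Medications form that starts during the episode and has the exacerbation as its reason for use. Classify blind before database lock, and report how many events enter by each route. Two linked points need attention. The 14-day merging rule in SAP 4.7.4 runs from the end of systemic antibiotics, which such an episode does not have, so the episode resolution date should be used there. The blind review should also check whether the single Preferred Term excludes these episodes, and how the discounting of other causes is to be judged. The cost is a modest SAP edit, some programming and blinded review time. The medication dates and reason for use are already collected.

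(b) Keep the algorithm. Reword the alternative definition in SAP 2.1, and relabel Table 14.2.1.1.3 as antibiotic-treated episodes under altered symptom and duration criteria. This costs a text change only, and gives up any claim about the prescribing criterion.

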4.7.4.2 CCI Analysis for Missing Data

In order to assess the potential impact of missing data on the results of the primary efficacy analysis, Copy Reference and Tipping Point CCI analyses using multiple imputation (MI) will be performed on all mITT subjects based on the approach proposed by Keene et al. [1].

Since Promis II was curtailed early, not all subjects are expected to have 365 days follow-up as intended in the original trial design. The expected duration of exposure for some subjects will therefore be shorter than 365 days. Therefore, and prior to unblinding, the expected duration of exposure in years, t_j , will be determined for each subject, $n = 1 \dots j$, individually using their randomisation date, r_j , and the date of study closure, d , where $d = 28\text{FEB}2022$ and $t_j = \min([d - r_j + 1]/365.25, 365/365.25)$. For all subjects with a realised follow-up duration, f_j , shorter than t_j , ie. with $f_j < t_j$, for example, due to early withdrawal or dropout

CONFIDENTIAL

Sponsor:	Zambon S.p.A.	Protocol Number:	Z7224L02
----------	---------------	------------------	----------

at time f_j relative to randomisation, the number of pulmonary exacerbations in the missing period of follow-up, $t_j - f_j$, will be imputed.

The number of potentially missing exacerbations per subject will be imputed to include the following variables: treatment, country, as detailed in Section 4.9.1, and use of stable concomitant therapy with oral macrolides.

The imputation will be performed according to the following strategies:

- (1) Copy reference: imputation of missing data in both randomised treatment groups based on the data distribution of data observed in the placebo group. This analysis mimics the case where discontinued subjects who were randomised to colistimethate sodium are assumed to instantaneously transition to placebo and lose any effect conferred by colistimethate sodium.
- (2) Tipping Point Analysis. For this analysis, discontinued subjects who were randomised to colistimethate sodium or placebo are initially imputed assuming the best case that data are missing at random and the treatment effect, CI and p-value are extracted. The analysis is subsequently repeated but now applying a small detrimental effect, δ , in the imputation of colistimethate sodium subjects with missing data and, again, the treatment effect, CI and p-value are extracted. This analysis is then repeated with an increasing penalisation of colistimethate sodium treated subjects by addition of a detrimental effect, 2δ , 3δ , ..., $k\delta$ in order to find the 'Tipping Point' being that degree of penalisation that leads to loss of statistical significance on the primary endpoint analysis.

A total of 20 imputed datasets will be generated with each analysed using the same NB model as described for the primary analysis. Log event rate and log event rate ratio estimates and associated SEs arising from these 20 imputed datasets will then be combined via PROC MIANALYZE using Rubin's rules ^[2].

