3.9 Sample Size

The sample size has been calculated considering the results from the previous trial (CCI [REDACTED]), relevant literature and the clinically meaningful benefit the treatment should provide. A treatment difference of CCI [REDACTED] between the colistimethate sodium and placebo groups CCI [REDACTED].

For the purpose of the power calculation, a simulation of exacerbations has been carried out by randomly assigning a patient a value CCI [REDACTED] according to the treatment group they are in and then generating a CCI [REDACTED] event rate using this parameter. This CCI [REDACTED] leads to two negative binomials with the following parameter values:

Placebo: mean CCI [REDACTED], variance CCI [REDACTED]

Colistimethate sodium: mean CCI [REDACTED], variance CCI [REDACTED].

These are rates per year. Note that, since the variances are greater than the mean, this means that there is mild over-dispersion.

Under these assumptions, CCI [REDACTED] allowing for over-dispersion for frequency of exacerbation (FOE), with a two-sided significance level of CCI [REDACTED], a treatment effect of CCI [REDACTED] and a follow-up time of 1 year, assuming a frequency of CCI [REDACTED] pulmonary exacerbations per annum

CONFIDENTIAL

Sponsor:	Zambon S.p.A.	Protocol Number:	Z7224L02
----------	---------------	------------------	----------

for the FOE, a sample size of 170 completed subjects per group will provide a power of 90% (simulated in [REDACTED]). If the treatment effect size is [REDACTED] between the colistimethate sodium and placebo groups, the power with [REDACTED] completed patients per group will be [REDACTED].

Assuming a drop-out rate of about 20%, the total sample size should be 210 subjects per treatment group (420 total subjects).

In November 2021, recruitment to PROMIS II was stopped based on the very positive data from PROMIS I, giving rise to ethical concerns of continuing to expose subjects to placebo in PROMIS II, the potential loss of scientific equipoise in the context of the PROMIS I results, and PROMIS II being unable to complete in a reasonable time frame, primarily related to the COVID-19 pandemic.

At the time that recruitment into PROMIS II was stopped, 287 of the originally planned 420 had been randomised. All subjects will be brought back for Visit 7 or an early termination visit on or before the end of February 2022.

CONFIDENTIAL

Sponsor:	Zambon S.p.A.	Protocol Number:	Z7224L02

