SET dataset4act_mar dataset4plb;
BY Iteration Subject;
RUN;

DATA dataset4all_cr; /* For Copy Reference */
SET dataset4act_cr dataset4plb;
BY Iteration Subject;
RUN;

DATA dataset5_mar; /* Missing at Random */
SET dataset4all_mar;
BY Iteration Subject;
ARRAY c[*] c_psite_d1-c_psite_dx c_med_d;
ARRAY x[*] psite_d1-psite_dx med_d;
k=1/Dispersion;
imp_subj=(years<365/365.25);
years_imp=MAX(years,years_exp);
log_years_imp=LOG(years_imp);
linpred_1=.;
IF imp_subj THEN DO;
years_miss=years_imp-years;
linpred_1=Intercept;
DO i=1 TO DIM(c);
linpred_1+c[i]*x[i];
END;
linpred_mar=linpred_1+c_treatment_d*treatment_d;
y2hat_mar=years_miss*EXP(linpred_mar);
CALL STREAMINIT(3231212);
y2_mar=RAND('NEGBINOMIAL',k/(k+y2hat_mar),k);
y_imp_mar=count+y2_mar;
END;
ELSE DO;
y_imp_mar=count;
END;
RUN;

DATA dataset5_cr; /* Copy Reference */
SET dataset4all_cr;
BY Iteration Subject;
ARRAY c[*] c_psite_d1-c_psite_dx c_med_d;

```

CONFIDENTIAL

Sponsor:	Zambon S.p.A.	Protocol Number:	Z7224L02
----------	---------------	------------------	----------

```

ARRAY x[*] psite_d1-psite_dx med_d;
k=1/Dispersion;
imp_subj=(years<365/365.25);
years_imp=MAX(years,years_exp);
log_years_imp=LOG(years_imp);
linpred_1=.;
IF imp_subj THEN DO;
  years_miss=years_imp-years;
  linpred_1=Intercept;
  DO i=1 TO DIM(c);
    linpred_1+c[i]*x[i];
  END;
  linpred_cr=linpred_1+c_treatment_d;
  y2hat_cr=years_miss*EXP(linpred_cr);
  CALL STREAMINIT(3231212);
  y2_cr=RAND('NEGBINOMIAL',k/(k+y2hat_cr),k);
  y_imp_cr=count+y2_cr;
END;
ELSE DO;
  y_imp_cr=count;
END;
RUN;

```

Notes:

- dataset1 includes one record per patient;
- count represents the total number of **CCI** t;
- treatment represents the treatment group (treatment order: 1 = colistimethate sodium, 2 = placebo);
- treatment_d represent the dummy variables for treatment group (values of the dummy variables: 0 for colistimethate sodium; 1 for placebo);
- Psite represents the country, as detailed in Section 4.9.1;
- psite_d1-psite_dx represent the dummy variables for the country;
- Med represents use of stable concomitant therapy with oral macrolides (e.g. azithromycin or erythromycin or clarithromycin) (Yes/No);
- med_d represents the dummy variable for use of stable concomitant therapy with oral macrolides;
- years represents the observed follow-up time in years;
- years_exp represents the expected follow-up time in years
- log_years represents the logarithm of the follow-up time in years.

Analysis step

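### Missing-data sensitivity analyses: expected exposure runs to a common 28 February 2022, so colistimethate subjects whom the sponsor closed out before that date and before day 365 are imputed and penalised like dropouts

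*SAP*

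**What the plan says.** SAP 3.9 states that "In November 2021, recruitment to PROMIS II was stopped", at which point "287 of the originally planned 420 had been randomised", and that "All subjects will be brought back for Visit 7 or an early termination visit on or before the end of February 2022".

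SAP 4.7.4.2 then sets up copy-reference and tipping-point analyses by multiple imputation. It recognises the curtailment ("The expected duration of exposure for some subjects will therefore be shorter than 365 days") and determines expected exposure t_j "individually using their randomisation date, r_j , and the date of study closure, d , where" d = 28FEB2022 and t_j = min([d − r_j + 1]/365.25, 365/365.25). Every subject whose realised follow-up f_j is below t_j has the period t_j − f_j imputed; dropout is given only as an illustration ("for example, due to early withdrawal or dropout"). Under copy reference, discontinued colistimethate subjects are "assumed to instantaneously transition to placebo and lose any effect conferred by colistimethate sodium". In the tipping-point analysis, a growing detriment is added to colistimethate subjects with missing data.

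The code in SAP 4.14 flags subjects with "imp_subj=(years<365/365.25" and takes the larger of observed and expected years as the target. It has no variable for why follow-up ended. SAP 3.6 does list termination of the trial by the sponsor among the withdrawal reasons and requires the reason to be recorded.

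**The concern.** Expected exposure was shortened so that curtailment would not count as missing data. The rule achieves this only for subjects whose close-out visit fell on the last permitted day. Anyone seen sooner, and not yet at 365 days, still shows a gap between f_j and t_j that the sponsor's scheduling created.

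That gap says nothing about why patients leave treatment. Giving it placebo rates, or adding the detriment, tests no hypothesis about withdrawal. Section 4.7.4.2 itself describes the affected group as discontinued subjects, yet the rule catches everyone with f_j < t_j. At stake is how the two analyses are read. Some of the copy-reference attenuation would come from scheduling, and the tipping-point detriment would be spread over a wider group than true dropouts.

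**Working it through.** The plan gives no figure for this point, so the rule is first evaluated by date and then sized under stated assumptions.

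**1. The rule by date.** In days, t_j = min(28 Feb 2022 − r_j + 1, 365) and f_j = min(visit date − r_j + 1, 365). The visit dates are illustrative. The cells show the days imputed for a subject on treatment until close-out or day 365.

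| Randomised | t_j | 1 Dec 2021 | 15 Jan 2022 | 14 Feb 2022 | 28 Feb 2022 |
|---|---|---|---|---|---|
| 1 Jun 2020 | 365 | 0 | 0 | 0 | 0 |
| 1 Mar 2021 | 365 | 89 | 44 | 14 | 0 |
| 1 Jun 2021 | 273 | 89 | 44 | 14 | 0 |
| 1 Sep 2021 | 181 | 89 | 44 | 14 | 0 |

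A subject with a full 365 days is never affected. For the others, the imputed time is the interval from their own visit to 28 February.

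**2. Dispersion for the sizing.** The dispersion k is redacted, so it is assumed. The protocol summary gives 170 completed per group, a placebo rate of 1.09 per year, two-sided 0.05, and power of 90% for a 35% effect and 80% for a 30% effect. With variance of the log rate ratio (1/1.09 + 1/(1.09·RR) + 2k)/170, k = 0.3 gives 90.7% and 79.0%. It is therefore consistent with the plan.

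**3. Simulation.** Assumptions: 287 subjects (143 on colistimethate), uniform accrual from March 2018 to mid-November 2021, true rate ratio 0.65, k = 0.3, no true dropout, and close-out dates uniform from the start shown to 28 February 2022. There were 300 replicates with 5 imputations each.

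| Close-out visits from | Colistimethate subjects imputed | Person-years imputed in that arm | Observed-data ratio | Copy-reference ratio |
|---|---|---|---|---|
| 1 Dec 2021 | about 32 | 3.7 | 0.643 | 0.653 |
| 15 Jan 2022 | about 29 | 1.7 | 0.648 | 0.653 |
| 14 Feb 2022 | about 26 | 0.5 | 0.647 | 0.648 |
| all on 28 Feb 2022 | 0 | 0 | 0.655 | 0.655 |

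The shifts are about +0.010, +0.005, +0.001 and 0. In the first scenario, the share of replicates reaching significance went from 84% to 83%. The last row shows that with no gap and no dropout, copy reference returns the observed-data estimate.

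**4. With true withdrawal included.** Assume 44 months of uniform accrual, with the last nine months supplying subjects short of a year: 287 × 9/44 ≈ 59. Mean gaps of 30, 45 and 75 days add 59 × gap/365 = 4.8, 7.3 and 12.1 patient-years over both arms. Against an assumed 28 patient-years from true withdrawal, that is 15%, 21% and 30% of all imputed time (for example 4.8/32.8). In the active arm, assume 122 observed and 14 withdrawn patient-years, and add half of the gap time:

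- no gap: (0.65 × 122 + 14)/136 = 0.686
- 30 days: (79.3 + 16.4)/138.4 = 0.692
- 45 days: (79.3 + 17.6)/139.6 = 0.694
- 75 days: (79.3 + 20.1)/142.1 = 0.699

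The shifts are 0.006 to 0.013, or 2% to 5% of the log effect.

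**5. A deliberate extreme.** Suppose 60 colistimethate subjects each had a 90-day gap. That is 14.8 imputed person-years, 13.85% of the arm's total, and the ratio is 0.65 × 0.8615 + 0.1385 = 0.699, a shift of about 0.05. This needs roughly twice the number of affected subjects that uniform accrual gives, all seen around 1 December.

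**The case against.** The strongest reply is that the SAP has already allowed for curtailment, that a single date fixed before unblinding avoids relying on an investigator's recorded reason, and that the distortion is conservative and confined to supporting analyses. All of that is fair, and it is why the point is minor. The reliance on recorded reasons is a real cost: a departure prompted by news of the sister trial could be coded as study closure and hide informative withdrawal.

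The definition of f_j is also unsettled. SAP 4.1.7 defines exposure time, ending at the treatment visit, separately from follow-up time, ending at study completion. Section 4.7.4.2 and the code notes speak of follow-up. If f_j includes the phone call about two weeks after treatment, each gap shrinks by about 14 days (89 to 75, 44 to 30, 14 to 0). The tables above use exposure time, in line with the window in which exacerbations are counted.

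Several stronger readings are tempting, but the documents do not support them:

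- That expected exposure runs to 28 February 2022 for everyone. The 365-day cap applies to anyone randomised on or before 1 March 2021.
- That close-out visits began in November 2021. SAP 3.9 dates only the recruitment stop then; for visits it gives a deadline, with no start date or counts.
- That the code flag alone creates imputed time. Taking the larger of observed and expected years leaves zero missing time for anyone who reached t_j.
- That completers seen in the week before day 365 are materially affected. At most 7 days are involved, about 1.09 × 7/365.25 = 0.02 events at the planned placebo rate, and none if f_j includes the phone call.
- That the analyses no longer test informative withdrawal. In step 4, true withdrawal still supplies 70% to 85% of imputed time.

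**Conclusion.** The point holds in limited form. With one common d and no reason for ending in the text or code, a colistimethate subject closed out by the sponsor before both 28 February 2022 and day 365 is imputed as if withdrawn, and receives placebo rates or the detriment. Placebo subjects are imputed too, but without penalty. The primary model uses observed exposure as its offset and does not change.

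The size cannot be known from the documents. Under uniform accrual and the other assumptions shown, the copy-reference rate ratio moves towards 1 by about 0.001 to 0.013; if visits clustered at the deadline, it hardly moves. A reader might infer that the tipping point is reached materially too early. The direction follows from penalising more subject-time, but no tipping-point calculation was run, so no size can be claimed. Severity is minor; confidence in the mechanism is high, and in the magnitude low.

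**What to change.** In SAP 4.7.4.2, keep t_j = min(d − r_j + 1, 365 days) for subjects who withdrew for other reasons. For subjects whose documented reason for ending is sponsor study closure, set t_j = f_j, so that nothing is imputed. Carry the same rule into SAP 4.14 through `imp_subj` and `years_exp`.

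The date d must stay for true withdrawals. Without it, a subject randomised on 1 September 2021 who withdrew in November would be imputed to day 365 instead of day 181, well past study closure.

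The cost is one derivation from the disposition reason, made at the step before unblinding where the SAP already determines t_j; no treatment codes are needed. The sensitivity analysis becomes slightly less conservative and depends on the recorded reason. Reporting the present common-date version alongside answers both objections. Label: cheap improvement.
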